3.4 Anti-Myeloma Treatment Following Descartes-11

After all Descartes-11 infusions and the Day 28 response assessment are completed, further anti-myeloma treatment can be administered. The treatment choice is left to investigator's discretion. If the patient is eligible for transplant, high dose chemotherapy and ASCT can be given. Patient will be followed-up during this period to evaluate the clinical outcomes for secondary objectives.

4 Protocol Evaluation and Biospecimen Collection

4.1 Study Procedures

4.1.1 Baseline Evaluation (Day -60 to Day 0)

1. Obtain informed consent
2. Review of records for documentation of high-risk multiple myeloma (R-ISS Stage III or at least one of the following: t(4;14), t(14;16), t(14;20), del(17/17p), del13, gain 1q, non-hyperdiploid karyotype)
3. Complete medical history and physical examination, including, height, weight and vital signs (should always include pulse oximetry unless stated otherwise), and ECOG performance score.
4. Concomitant medications
5. Complete blood count, differential
6. Chemistry panel (Glucose, Ca, Mg, Phos, Alk Phos, Albumin, Total Protein, Total Bilirubin, K, Na, Cl, HCO₃, BUN, Uric Acid, Cr, ALT, AST, lactate dehydrogenase)
7. PT/INR, PTT
8. D-Dimer, fibrinogen
9. Urinalysis
10. CRP, ferritin
11. β₂-microglobulin
12. Infectious Panel: Hepatitis B Surface Ag (HBsAg), Hepatitis B Core Total Ab, Hepatitis C Virus Ab (anti-HBc), HIV-1/HIV-2 Ab
13. Lymphocyte sub-set counts (CD19, CD3, CD4, CD8, CD56)
14. Serum protein electrophoresis (SPEP) and serum immunofixation electrophoresis (SIFE)
15. 24-h urine for urine protein electrophoresis (UPEP) and urine immunofixation electrophoresis (UIFE)
16. Serum free light chain (FLC) assay
17. Unilateral bone marrow aspirate + biopsy, including bone marrow immunohistochemistry and bone marrow flow cytometry
18. If the prospective subject has known or suspected extramedullary plasmacytomas, previous imaging results will be reviewed to confirm the status of the lesions and a repeat imaging (i.e., CT scan) can be done if the principal investigator deems it necessary to document the size/scope of the lesion.
19. ECG
20. ABO typing
21. Echocardiogram to assess left ventricular function if not performed within the last 6 months
22. β- HCG for all women of child-bearing potential. Female subjects of reproductive potential (women who have reached menarche and who have not been post-menopausal for at least 24 consecutive months, i.e., who have had menses within the preceding 24 months, or have not undergone a sterilization procedure (hysterectomy or bilateral oophorectomy) must have a negative serum pregnancy test performed at the time of screening and must agree not to participate in a conception process (e.g., active attempt to become pregnant or to impregnate sperm donation or *in vitro* fertilization) until 4 months after receiving preconditioning chemotherapy. Additionally, if participating in sexual activity that could

lead to pregnancy, the subject must agree to use a reliable method of contraception during their participation in the study (e.g., condoms (male or female) with or without a spermicidal agent, diaphragm or cervical cap with spermicide, or intrauterine device (IUD)).

23. Research blood (See Laboratory Manual for collection details)

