The potency of virally transduced CAR therapies comes with significant risks. All clinical trials of virally transduced CAR T-cells have recorded serious instances of cytokine release syndrome (CRS) and neurological toxicity. In the recent American Society of Blood and Marrow Transplant (ASBMT) consensus meeting, CRS was defined as “a supraphysiologic response following any immune therapy that results in the activation or engagement of endogenous or infused T cells and/or other immune effector cells. Symptoms can be progressive, must include fever at the onset, and may include hypotension, capillary leak (hypoxia) and end organ dysfunction.”⁴¹ CRS is a prototypical systemic inflammatory response syndrome that occurs hours to days after CAR T-cell infusion. Signs and symptoms include fever, myalgia, malaise, and, in more severe cases, a capillary leak syndrome associated with hypoxia, hypotension, and occasionally renal dysfunction and coagulopathy. Peak CAR T-cells as a result of *in vivo* proliferation has been strongly associated with the severity of CRS in many CAR T-cell studies.^{42,43} The proliferation of CAR T-cells upon engagement with target antigen drives them to secrete cytokines that initiates a cascade of systemic inflammatory events. Among all cytokines elevated during CRS, IL-6 plays a central role as neutralization of this cytokine quickly and effectively reverses clinical deterioration in most cases.

The first presenting symptom of CRS is usually fever associated with mild constitutional symptoms.^{42,44-46} In a number of patients, the initial mild symptoms progress over the course of hours to days and turn into a systemic inflammatory syndrome characterized by sinus tachycardia, hypotension and hypoxia. In severe cases, patients may require mechanical ventilation and vasopressors. CRS can start as early as the day of CAR T-cell infusion and in most cases it occurs within the first 14 days following the infusion. Severe cases appear to occur closer to the time of infusion and the severity of CRS was reported to correlate with peak CAR T-cell levels as mentioned above as well as disease burden^{42,43} and addition of preconditioning chemotherapy.^{43,44,46,47}

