3.2.1 Overall Treatment Design

The overall schedule of treatment for this Phase II study is illustrated in [Figure 1](#). Steps shown prior to Screening affect eligibility but are not part of the study.

Eligible patients will receive an induction regimen with at least 2 anti-myeloma agents excluding monoclonal antibodies. After completion of the full pre-transplant induction regimen prior to high-dose chemotherapy and ASCT, eligible patients must have measurable residual disease as defined in the Eligibility Criteria. A patient can be screened and enrolled at that point.

Descartes-11 treatment will begin at least 7 days after the patient's final dose of anti-myeloma therapy. The dose of cells will be 25×10^6 cells/kg, and doses will be given on Days 1, 4, 8, 11, 15, 18 (i.e., total dose of 150×10^6 cells/kg). Weight obtained during Screening Visit will be used for dose calculation. Doses are expressed as the number of live CAR+ cells.

After completing all cell infusions, the patient will be evaluated for clinical response and then followed-up for up to 36 months unless they meet off-study criteria outlined in [Section 4.5.2](#). During the follow-up period, if indicated, any additional induction therapy, high-dose chemotherapy and/or ASCT may be administered at the discretion of the investigator. Except for experimental agents that are not approved for myeloma treatment, treatment will be left to the investigator's discretion. The patient will be followed every 3 months for the first year, every 6 months for the second year and one time during the third year.

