3.2.2 Delay of Cell Infusion

Patients experiencing toxicities from their preceding treatments will have their Descartes-11 infusion schedule delayed until these toxicities have resolved to at least Grade 2 (excluding cytopenias), unless in the documented opinion of the medical monitor and treating physician it is reasonable to proceed. During this period, the patient will be assessed to record adverse events and a decision will be made on whether the patient meets criteria for cell infusion. Infusions can also be delayed up to 24 hours for scheduling reasons. Furthermore, prior to study cell infusion, subjects must have been free from fever, infection and organ dysfunction since qualifying for the study (See [Section 3.3.1.2](#) for details). If the patient does not meet infusion criteria, the infusion can be delayed up to 4 weeks.

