4.5.2 Criteria for Off-Study

Patients will be taken off study for the following:

- The patient voluntarily withdraws
- There is significant patient noncompliance
- Death
- Development of progressive or relapsed MM after completing Descartes-11 infusions

Patients must be followed until all adverse events have resolved to grade 2 or less other than lymphopenia or alopecia. If an adverse event is not expected to resolve to Grade 2 or less, this will be noted in the patient medical record and the patient will be taken off-study. Patients, upon obtaining consent, will also be followed for additional clinical outcomes like overall survival.

5 Safety, Adverse Events, Protocol Deviation and Stopping Rules

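### The no-conception rule in Section 4.1.1 item 22 is timed from a preconditioning chemotherapy that the readable protocol never schedules, so it has no end date

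*Combined protocol and SAP*

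**What the plan says.** Item 22 of Section 4.1.1 sets two duties for women of reproductive potential.

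- **Conception.** At screening the woman "must agree not to participate in a conception process" "until 4 months after receiving preconditioning chemotherapy".
- **Contraception.** If she has sexual activity that could lead to pregnancy, "the subject must agree to use a reliable method of contraception during their participation in the study".

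Section 3.2.1 describes a washout of at least 7 days from the last anti-myeloma therapy, after which "doses will be given on Days 1, 4, 8, 11, 15, 18". If the infusion criteria are not met, "the infusion can be delayed up to 4 weeks" (Section 3.2.2). After the Day 28 assessment, further anti-myeloma treatment is at the investigator's discretion: "If the patient is eligible for transplant, high dose chemotherapy and ASCT can be given" (Section 3.4).

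Study participation ends on voluntary withdrawal, significant noncompliance, death, or "Development of progressive or relapsed MM after completing Descartes-11 infusions" (Section 4.5.2).

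Section 8 lists cyclophosphamide, fludarabine and tocilizumab as drugs that sites obtain commercially.

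**The concern.** A restriction with a stated length needs a starting event for the clock. Here that event is a treatment the readable plan does not give. The duty begins at screening, but nothing in the schedule starts the 4 months.

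While a woman stays on study, the contraception duty covers unintended pregnancy. The gap opens if she leaves within weeks or a few months of her last infusion. Contraception then lapses with participation, and the conception agreement has no date on which it ends. The follow-up visits in Section 4.1.4 include no pregnancy test, so after Day 28 her own agreement is the main preventive measure left. Section 7.2 says it is not reasonable to give a previously uncharacterised cell therapy to pregnant or lactating women, so the protocol itself treats exposure in pregnancy as something to avoid.

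**Working it through.** **Step 1: look for the anchor event.**

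| Place | What it contains | Preconditioning chemotherapy? |
|---|---|---|
| 3.2.1 Overall Treatment Design | Washout of at least 7 days, then six infusions | No |
| 3.3.1.2 Drug Administration | Infusion criteria; premedication with acetaminophen and diphenhydramine | No |
| 4.1.2 Infusion visits | Assessments before and after each infusion | No |
| 4.2 Study Calendar | Screening, then Day 1 directly | No |
| 1.2.5 Background | CRS severity in other CAR T-cell studies, linked to disease burden "and addition of preconditioning chemotherapy" | Mentioned, but not as a step of this trial |
| 3.4 Treatment after Descartes-11 | Optional high-dose chemotherapy and ASCT after Day 28 | Not called that |
| 8 Pharmaceutical Information | Cyclophosphamide and fludarabine named, with no dose, day or purpose | No step described |

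No readable part of the treatment plan contains the event. The stated 4 months can be read, but the date on which they end cannot be derived.

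**Step 2: test the reading that gives the phrase a meaning.** Suppose item 22 means the conditioning before ASCT. That treatment is optional and comes after Day 28. The end date would then vary between women, and for those not transplanted there would be none.

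**Step 3: compute the end date if the 4 months ran from the last infusion received.** Assumptions: one month is 365.25/12 days, and a delayed infusion shifts all later ones by the same amount.

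- 4 months = 4 × 365.25/12 = 121.75 days.
- End day = day of last infusion received + 121.75.

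| Case | Last infusion | End of restriction |
|---|---|---|
| Only the first dose given | Day 1 | 1 + 121.75 = about Day 123 |
| On schedule | Day 18 | 18 + 121.75 = about Day 140 |
| One 4-week delay | 18 + 28 = Day 46 | 46 + 121.75 = about Day 168 |
| Two 4-week delays | 18 + 56 = Day 74 | 74 + 121.75 = about Day 196 |

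The table has no natural upper limit. The infusion criteria apply before every dose, Section 3.2.2 does not say how many delays are allowed, and Section 4.5.1 refers to possible repeat treatment and to cycles. What the anchor provides is a date that can be calculated for every treated woman.

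**The case against.** **The step may sit in text that cannot be seen.** Section 1.3.2, which covers the dosing regimen, is redacted; 3.3.1.1 is blank and Figure 1 is missing. This stands as a caveat. However, the treatment design, infusion visits and calendar are readable, and a chemotherapy step would be expected there.

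**The practical gap is narrow.** This largely stands. Pregnancy is an exclusion, and tests are done at screening, before each infusion and at Day 28. Contraception is required throughout participation, with follow-up of up to 36 months. For a woman on schedule who stays past about Day 140, that duty outlasts the 4 months. Consenting women who withdraw early can have data collected for up to one year (Section 2.2.5), and a congenital anomaly in later offspring is to be notified to the sponsor (Section 5.2.1). These last two provisions collect information afterwards; neither sets an end date.

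**Nothing readable supports 4 months for this product.** This stands. Appendix B, Section 1.2.2 gives a half-life for CAR expression, and a reader might take it as support for 4 months. It describes CAR expression and is not a reproductive-safety margin. The 4 months is only a default carried over from the protocol's own text.

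**Stronger readings that the documents do not support.**

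- A reader might infer that sites cannot tell women when the restriction ends. The consent pages were removed from the reviewed copy, so what women are told is unknown.
- A reader might infer that ASCT conditioning is the only chemotherapy the plan allows. Section 3.2.1 also permits additional induction therapy during follow-up, with the drugs unspecified.
- A reader might infer that the re-anchored date always falls between the Month 3 and Month 6 visits. With two delays it is about Day 196, past Month 6 (6 × 365.25/12 = 182.6 days, about Day 183 counted from Day 1).
- A reader might take the Section 8 drug list as evidence of harm or of a hidden regimen. It says only how the drugs are obtained and instructs nobody to give them.

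**Conclusion.** Wrong as written; minor, patient safety. On the readable text, the no-conception rule depends on an event that is not part of the trial, so it has no end date. Reading it as transplant conditioning leaves women who are not transplanted without one. The consequence is confined to women of child-bearing potential who leave the study soon after dosing. The documents do not say how many such women are expected among the 34 planned patients, and there may be none.

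No endpoint, sample size or analysis is touched. The conclusion assumes that the hidden parts contain no preconditioning step. If they do, the defect becomes one of omission from Section 3.2.1 and the calendar. The surplus drugs in Section 8 are a housekeeping matter and add no weight to the safety point.

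**What to change.** 1. In item 22, end the conception restriction 4 months after the last Descartes-11 infusion received, including any repeat treatment. Keep 4 months unless the sponsor justifies another duration for this product.
2. In the same item, run the contraception duty at least to that date, whether or not the woman is still on study.
3. As a consistency clean-up only, delete cyclophosphamide and fludarabine from Section 8. Keep tocilizumab, which Appendix A uses for CRS.
4. If preconditioning is in fact intended, do not make the Section 8 deletion. Add the step to Section 3.2.1 and the calendar with drugs, doses and days.

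Items 1 to 3 amend two sentences and one drug list, and the consent form should be checked against them. They change no dosing, visit, sample size or endpoint. Item 4 would be a larger amendment, but it would only write down what was already meant.

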4.1.2 Descartes-11 Infusion (Days 1,4, 8, 11, 15, 18)

If not performed in the past 7 days and within one day of the first Descartes-11 infusion at least one of the following should be performed if abnormal at screening:

- Serum protein electrophoresis (SPEP) and serum immunofixation electrophoresis (SIFE);
- 24-h urine for urine protein electrophoresis (UPEP) and urine immunofixation electrophoresis (UIFE);
- Serum free light chain (FLC) assay

Prior to infusion of cells, the following assessments must be completed:

1. Medical history for adverse events
2. Vital signs including pulse oximetry and physical exam including brief neurological exam
3. Concomitant medications
4. ECOG performance status
5. Urine pregnancy test for all women of child-bearing potential
6. Research Blood (See Laboratory Manual for collection details)

Only on Days 1, 8, 15 the following laboratory assessments will be also be performed prior to infusion:

1. Chemistry panel (Glucose, Ca, Mg, Phos, Albumin, Total Protein, Total Bilirubin, K, Na, Cl, HCO₃, BUN, Cr, ALT, AST, lactate dehydrogenase)
2. CRP, ferritin
3. Urinalysis

Complete blood count, differential

After infusion of cells, the following assessments must be completed:

1. Within 5±2 min of completing each infusion, Research blood should be collected. See Laboratory Manual for collection details.
2. Vital signs (See [Section 3.3.3](#) for details)

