2.1 Eligibility Criteria

2.1.1 Inclusion Criteria

The following inclusion criteria will be applied at Screening, unless another evaluation time point is specified:

1. High-risk multiple myeloma patients (defined below) who complete pre-transplant induction treatment anti-myeloma drug combination (minimum 2 drugs).
2. Following completion of the pre-transplant induction regimen, patients must have residual disease measured by at least one of the following markers:
 - a. Serum M-protein detectable by immunofixation
 - b. Urine M-protein detectable by immunofixation
 - c. Abnormal FLC ratio
 - d. A biopsy-proven plasmacytoma or residual disease on imaging of a spot that was known to have plasmacytoma
 - e. Evidence of clonal cells in immunohistochemistry defined as Kappa/Lambda <4:1 or >1:2 after counting ≥ 100 plasma cells
 - f. Evidence of MRD detected by DNA-based or flow cytometry approaches
3. Patients must have high-risk multiple myeloma based on IMWG consensus as defined by R-ISS Stage III¹⁰ or high-risk CA³.
 - a. R-ISS Stage III is defined as having serum β -microglobulin ≥ 5.5 mg/L and either a high risk CA by iFISH or high LDH.
 - b. High-risk CAs are defined as having 1) t(4;14), t(14;16), t(14;20), or del(17/17p) in at least 20% of the cells; 2) any non-hyperdiploid karyotype, 3) gain(1q); 4) del 13; 5) gain 1q; or 6) a high-risk signature on gene expression profile (GEP).
4. There should be at least 7 days between the last dose of anti-myeloma drug and first Descartes-11 infusion.
5. Toxicities from prior therapies must have resolved to Grade 2 or less according to the CTCAE 5.0 criteria, or to the subject's pre-therapy baseline at the time of first cell infusion.
6. Patients must have signed written, informed consent.
7. Patients must be 18 years of age or older at the time of enrollment.
8. Patients must have clinical performance status of ECOG 0-2.
9. Patients must be seronegative for HIV.
10. Patients must be seronegative for hepatitis B (HBV) antigen; or, if the patient is positive for the hepatitis B antigen test, he or she must be negative for HBV DNA and must agree to use Hepatitis B prophylaxis as per institution guideline and/or principal investigator discretion.

11. Patients must be seronegative for hepatitis C (HCV) antibody; or, if the hepatitis C antibody test is positive, the patient must be tested for the presence of viremia by RT-PCR and must be HCV RNA negative.

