5.5 Stopping Rules and Study Termination

Premature termination of the clinical trial may occur because of a regulatory authority decision, change in opinion of the IRB or medical monitor. Additionally, recruitment may be stopped for reasons of particularly low recruitment, protocol violations, or inadequate data recording. Specifically, study will be stopped if:

- Study Sponsor or a Regulatory Body decides for any reason that subject safety may be compromised by continuing the study.
- The Sponsor decides to discontinue the development of the intervention to be used in this study.

The study will be **paused if:**

- There is death that is reasonably attributed to study drug within the first 30 days after first infusion
- Two subjects with Grade 4 adverse events to vital organs that are assessed as probably or definitely related to study drug within the 14 days after last infusion

If the study is paused for the reasons above, the PI and members of the study team will meet in person or by teleconference within 24 hours of the event to have a thorough discussion of the event. Meeting minutes capturing the review of any ongoing investigations, including next steps in the management of the subject and any proposed changes to the protocol will be forwarded to the medical monitor. If all parties agree as to the event resolution, then the pause will be lifted. If the study is paused for manufacturing reasons, the Sponsor will make recommendations for process improvements to be implemented. Pending successful completion of a process validation run, the manufacturing pause will be lifted.

6 Statistical Considerations

Statistical analysis will be described in a separate Statistical Analysis Plan.

Briefly, with respect to sample size: the primary endpoint will be the proportion of responders, i.e., patients who are MRD-negative with sCR at the Day 28 Visit. This is an open-label study, and the null hypothesis is that the responder rate will not differ from the natural rate of MRD-negative sCR at the end of consolidation, as observed in the literature. We determined that this natural rate is 10%.^{19,31,64,69-73} For purposes of power calculations, we assume that the response rate will be 35%. With these assumptions, a sample size of 34 will provide 80% power to detect a one-tailed difference at the 95% confidence level.

7 Ethical Considerations

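### Disease status at first infusion is not pinned down: residual disease may date from Day -60 and the pre-infusion recheck is minimal, so some Day 28 responses could reflect earlier remission

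*Combined protocol and SAP*

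**What the plan says.** **When residual disease is shown.** Section 2.1.1 applies the inclusion criteria at screening unless another time is named. Criterion 2 accepts any one of six markers (serum or urine immunofixation, FLC ratio, plasmacytoma, marrow immunohistochemistry, MRD), measured after the pre-transplant induction regimen is complete. Section 4.1.1 lets this evaluation take place anywhere from Day -60 to Day 0.

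**Drug before infusion.** Criterion 4 reads "There should be at least 7 days between the last dose of anti-myeloma drug and first Descartes-11 infusion". Section 2.1.2 excludes monoclonal antibodies and experimental agents before infusion and allows off-label use of other approved anti-myeloma drugs.

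**Recheck.** For the first infusion, unless done in the past 7 days, Section 4.1.2 says "at least one of the following should be performed if abnormal at screening". The list is SPEP/SIFE, 24-hour UPEP/UIFE and serum FLC. Note g of the Study Calendar (Section 4.2) likewise asks for one of them. The criteria to be met before each infusion (Section 3.3.1.2) cover temperature, infection, drug interval, toxicity, organ dysfunction and rapid progression. None asks whether residual disease is still present.

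**Endpoint and test.** In Section 6 responders are "patients who are MRD-negative with sCR at the Day 28 Visit". The comparison is with a fixed reference: "the null hypothesis is that the responder rate will not differ from the natural rate of MRD-negative sCR", set at 10%. On size, "a sample size of 34 will provide 80% power to detect a one-tailed difference at the 95% confidence level", assuming a 35% response rate.

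**The concern.** The trial has one arm, and the responder count is compared with a fixed 10%. No control group would show how many patients reach MRD-negative sCR without Descartes-11, whether from a continuing effect of induction or from an approved drug given after screening. The credit given to Descartes-11 therefore rests on patients still having disease when the first infusion is given.

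The protocol documents that status only at screening. A patient whose repeated marker is normal on Day 1 is handled no differently from one whose marker is abnormal. A patient who entered by marrow, MRD or plasmacytoma alone need not be rechecked at all. Any remission reached in the interval that persists to Day 28 counts in the numerator, so the responder rate can only be pushed upward.

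**Working it through.** **1. The plan's own figure.** Inputs from Section 6: p0 = 0.10, p1 = 0.35, one-sided alpha 0.05, power 0.80. The pooled two-proportion formula gives

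n = [1.645·√(2·0.225·0.775) + 0.842·√(0.10·0.90 + 0.35·0.65)]² / 0.25² = 33.4, rounded up to 34.

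This reproduces 34, but as a per-arm number for two arms. For the one-arm design, the exact binomial at n = 34 gives P(X ≥ 6 | 0.10) = 0.119 and P(X ≥ 7 | 0.10) = 0.048. The exact rule is therefore at least 7 responders, with power 0.978 at 35%. That mismatch is a separate matter, and the present point does not depend on it. Section 6 states no decision rule, so 7 of 34 is my assumption.

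**2. The interval.** Screening as early as Day -60 and last drug as late as Day -7 leave 60 − 7 = 53 days in which drug is not barred. Section 3.2.2 also allows infusion to be delayed up to 4 weeks and does not say whether baseline is then repeated.

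**3. Who is exposed.**

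| Status before first infusion | What the recheck shows |
|---|---|
| Repeated marker still abnormal | Patient is not in sCR; no exposure |
| Repeated marker normal | Remission possible; no rule follows, and other abnormal markers need not be repeated |
| Entry only by marrow, MRD or plasmacytoma | No recheck required |

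No marrow or MRD test is listed between screening and Day 28.

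**4. Effect on the test.** The documents give no rate of remission before Day 1, so the number k is assumed. Suppose k of 34 are already in MRD-negative sCR at Day 1 and stay so, and the others respond at 10%. The chance of success is then P(Bin(34−k, 0.10) ≥ 7−k):

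| k | Calculation | Chance of success |
|---|---|---|
| 0 | P(Bin(34, 0.10) ≥ 7) | 0.048 |
| 1 | P(Bin(33, 0.10) ≥ 6) | 0.106 |
| 2 | P(Bin(32, 0.10) ≥ 5) | 0.211 |
| 3 | P(Bin(31, 0.10) ≥ 4) | 0.376 |

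**5. If the 10% already includes such remissions.** They then add nothing until they exceed 10%. With a total rate of 10% the chance is 0.048; with 15% it is 0.241.

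**6. Power of a strict sensitivity analysis.** Counting k patients as non-responders under the same rule gives power P(Bin(34−k, 0.35) ≥ 7) = 0.972, 0.964, 0.954 and 0.941 for k = 1 to 4.

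**The case against.** **No drug is planned in the interval.** Residual disease must be shown after induction is complete, Section 3.2.1 places screening at that point, no bridging therapy is described, and Section 3.4 puts further treatment after the Day 28 assessment. This stands. A reader might infer that patients receive up to 53 days of other therapy after baseline. The documents do not say so; 53 days is the length of an interval without a prohibition. The gap is narrower for it but still open, because approved non-antibody drug is not barred and a late effect of induction is not ruled out.

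**Cleared markers are not a response.** A reader might infer that a patient whose blood and urine markers cleared before Day 1 is thereby a responder. That does not follow. Under Table 1, sCR also needs fewer than 5% marrow plasma cells and no clonal marrow cells, and the endpoint adds MRD negativity. This matters for size. If a share f of 3%, 5% or 10% cleared and all of them met the full endpoint, the rate f + (1−f)·0.10 would give a success chance of 0.132, 0.215 or 0.475. If half met it (illustrative; Section 1.2.3 reports one regimen in which half of the CRs were MRD-negative), the rate 0.5f + (1−f)·0.10 gives 0.079, 0.106 or 0.190. The higher set should not be read as an estimate.

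**The recheck is a minimum, and one abnormal result is enough.** Sites may do more, and a single marker still abnormal excludes sCR. Both stand. The weakness is confined to patients with a normal recheck or none.

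**The analysis plan may deal with it.** Section 6 refers to a separate Statistical Analysis Plan whose text is not in the document reviewed. A rule on Day 1 status could be there.

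**Conclusion.** The point holds in a limited form. As written, the protocol lets an MRD-negative sCR reached before the first infusion count as a Day 28 response, and it collects too little at Day 1 to tell how often that happens. The bias is upward and its size cannot be found from the documents. Under an assumed rule of at least 7 of 34, with the remaining patients at the 10% null and none of these remissions already inside that 10%, one to three such patients would raise the false-positive chance from 0.048 to between 0.11 and 0.38.

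A reader might go on to conclude that patients with cleared peripheral markers should be refused credit in the primary analysis. The documents do not support that. Criterion 2f admits patients whose only evidence of disease is MRD, and their conversion counts. A patient whose serum, urine and FLC markers have normalised may be in the same state on Day 1, so refusing credit would score identical patients differently by entry route and could discard real conversions. The issue belongs in measurement and sensitivity analysis.

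**What to change.** - In Section 4.1.2 and note g of the Study Calendar, replace the minimum of one test with a requirement to repeat each of the three assays that was abnormal at screening, within 7 days before first infusion. Use those values as the response baseline. The screening window need not change.
- Because the Day 28 assays in Section 4.1.3 are conditional on presence at baseline, state that any assay abnormal at screening is still run at Day 28 even if it was normal on Day 1.
- Keep the primary endpoint as defined. Report Day 28 responders by Day 1 peripheral-marker status: still abnormal, all normalised, or not assessable because entry was by marrow, MRD or plasmacytoma only.
- Pre-specify a sensitivity analysis that counts as non-responders those whose qualifying serum, urine and FLC abnormalities had all normalised before Day 1.

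Cost: one or two routine tests per patient, all already in the protocol, and possibly a lower sensitivity estimate. That estimate is conservative, since some of these patients may still have had marrow disease or MRD on Day 1. No larger sample is needed. Patients who entered only by marrow, MRD or plasmacytoma remain unassessed on Day 1, but the separate reporting makes their number visible. This is a cheap improvement.
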